Study Drug	ABT-450/ritonavir/ABT-267, ABT-333, ribavirin
Day 1	First day a subject took study drug
Treatment Period	Baseline/Day 1 through the last dose of study drug
Post-Treatment Period	Day after the last dose of study drug through Post-Treatment Week 260 or Post-Treatment Discontinuation

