In summary, the 3-DAA regimen, with or without RBV, was well tolerated with a low discontinuation rate. Adverse events were typically mild, and many of the adverse events and laboratory abnormalities observed were attributable to the presence of RBV. Transient, asymptomatic serum ALT elevations were observed at a low rate, were not associated with hepatic dysfunction and generally resolved with ongoing treatment.

A detailed discussion of the preclinical toxicology, metabolism, pharmacokinetics and drug-drug interactions can be found in the Investigator's Brochure for ABT-267, ABT-450, ABT-333 and product label for ritonavir and ribavirin.²⁵⁻²⁹

The current study is intended to evaluate the long-term outcomes with ABT-450/r/ABT-267 and ABT-333 with or without RBV for treatment-naïve and IFN/RBV treatment-experienced adults with chronic HCV GT1 infection, with or without compensated cirrhosis.

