6.3 Relationship to Study Drug

The investigator will use the following definitions to assess the relationship of the adverse event to the use of DAAs (ABT-450/r/ABT-267 and ABT-333) and to the use of RBV (if applicable):

Reasonable Possibility	An adverse event where there is evidence to suggest a causal relationship between the study drug and the adverse event.
No Reasonable Possibility	An adverse event where there is no evidence to suggest a causal relationship between the study drug and the adverse event.

[figure not shown]
For causality assessments, events assessed as having a reasonable possibility of being related to the study drug will be considered "associated." Events assessed as having no reasonable possibility of being related to study drug will be considered "not associated." In addition, when the investigator has not reported a causality or deemed it not assessable, AbbVie will consider the event associated.

If an investigator's opinion of no reasonable possibility of being related to study drug is given, an Other cause of event must be provided by the investigator for a serious adverse event.

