8.1.4.1 Adverse Events

Adverse events will be coded using the Medical Dictionary for Regulatory Activities (MedDRA). The number and percentage of subjects with treatment-emergent adverse events (i.e., any event that begins or worsens in severity after initiation of study drug through 30 days post-study drug dosing) will be tabulated by primary MedDRA System Organ Class (SOC) and preferred term (PT). The tabulation of the number of subjects with treatment-emergent adverse events by severity rating and relationship to study drug will also be provided. Subjects reporting more than one adverse event for a given MedDRA preferred term will be counted only once for that term using the most severe incident for the severity rating table and the most related for the relationship to study drug table. Subjects reporting more than one type of event within a SOC will be counted only once for that SOC.

Additional analyses will be performed if useful and appropriate.

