Treatment-emergent adverse events will be summarized by maximum severity grade level of each preferred term. Each preferred term will be assigned to a grade level based on severity and seriousness, adapted from the Division of AIDS (DAIDS) table for grading severity of adverse events. All serious adverse events will be categorized as Grade 4. Nonserious adverse events categorized by the investigators as mild, moderate, or severe will be categorized as Grade 1, Grade 2, or Grade 3, respectively. If a subject has a nonserious adverse event with unknown severity, then the subject will be counted in the severity grade level category of "unknown," even if the subject has another occurrence of the same event with a severity present. The only exception is if the subject has another occurrence of the same adverse event with the most extreme severity – "Severe." In this case, the subject will be counted under the "Grade 3" category. Similarly, if a subject has an adverse event with unknown seriousness, then the subject will be counted in the severity grade level category of "unknown" unless the subject has another occurrence of the same adverse event that is marked serious. In this case, the subject will be counted under the "Grade 4" category.

Adverse Event by Maximum Relationship

Treatment-emergent adverse events also will be summarized by maximum relationship of each preferred term to study drug (DAA), as assessed by the investigator. If a subject has an adverse event with unknown relationship, then the subject will be counted in the relationship category of "unknown," even if the subject has another occurrence of the same event with a relationship present. The only exception is if the subject has another occurrence of the same adverse event with a relationship assessment of "Reasonable

Possibility." In this case, the subject will be counted under the "Reasonable Possibility" category.

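### SAP 11.2.1.1 limits every relatedness summary to the DAAs, so the separate ribavirin causality judgement is never tabulated and the protocol's table by relationship to study drug is not delivered

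*SAP*

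**What the plan says.** **Protocol.** Section 1.3 defines study drug as "ABT-450/ritonavir/ABT-267, ABT-333, ribavirin". Section 6.3 asks the investigator "to assess the relationship of the adverse event to the use of DAAs (ABT-450/r/ABT-267 and ABT-333) and to the use of RBV", where RBV applies. Section 8.1.4.1 states that a tabulation of treatment-emergent "adverse events by severity rating and relationship to study drug will also be provided", and the synopsis says the same. Neither place narrows the term to the DAAs. On missing judgements, Section 6.3 says that "when the investigator has not reported a causality or deemed it not assessable, AbbVie will consider the event associated".

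**SAP 11.2.1.1.** Five outputs use relatedness: the overview, the table by system organ class (SOC) and preferred term (PT), the table by preferred term alone, the maximum-severity table and the maximum-relationship table. The first four refer to a reasonable possibility of relationship to the DAAs. In the fifth, events are "summarized by maximum relationship of each preferred term to study drug (DAA), as assessed by the investigator". For that fifth table the SAP adds: "If a subject has an adverse event with unknown relationship, then the subject will be counted in the relationship category of" *unknown*, unless another occurrence of the same event in that subject is rated a reasonable possibility. The listings in SAP 11.2.2 include none by relationship to RBV.

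**The concern.** The SAP replaces a defined protocol term with a narrower one and gives no reason. An anemia that the investigator links to RBV but not to the DAAs counts as related to study drug under the protocol, yet it appears as related in none of the SAP's summaries.

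RBV is also the component to which the protocol assigns much of the toxicity. Section 3.0 says that "many of the adverse events and laboratory abnormalities observed were attributable to the presence of RBV". A reader who wants the rate of events judged related to the regimen that subjects actually took would not find it in the report.

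Other outputs do not let the reader reconstruct it. SAP 5.1.2 pools subjects in one column whatever their RBV use, SAP 5.1.3 presents safety for all subjects together, and no adverse event table is split by RBV use.

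Separately, an event with no causality recorded is associated under one document and unknown in a table planned by the other.

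**Working it through.** There is no planned figure to reproduce. The check sets the two documents' rules side by side for each causality pattern an event can have.

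| Investigator's judgement | Protocol 1.3, 6.3, 8.1.4.1 | SAP 11.2.1.1 |
|---|---|---|
| Related to DAAs (RBV either way) | Related to study drug | Related |
| Not related to DAAs, related to RBV | Related to study drug | Not related in the maximum-relationship table; absent from the other four relatedness outputs |
| Related to neither | Not related | Not related |
| Not reported or not assessable | Associated | Unknown in the maximum-relationship table, subject to its exception; handling in the other four not stated |

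**Direction.** Among N treated subjects, let D be those with at least one event rated related to the DAAs, R those with at least one rated related to RBV, and M those with at least one event of missing causality.

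- SAP rate = |D| / N.
- Protocol rate = |D ∪ R| / N, or |D ∪ R ∪ M| / N if the 6.3 rule is applied in the tables.
- Gap = |R not in D| / N, plus |M not in D ∪ R| / N if the 6.3 rule is applied and missing causality is not already counted as related.

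Each term is zero or positive, so the SAP rate is equal to or lower than the protocol rate. It equals it when no subject's only related events are RBV-only or of missing causality. The documents give neither count, so the gap cannot be computed.

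**Is RBV attribution a realistic issue?** Protocol Table 3, regimen-controlled studies, 3-DAA + RBV minus 3-DAA:

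- anemia 7.5% − 0.2% = 7.3 points
- nausea 15.7% − 8.4% = 7.3 points
- insomnia 12.2% − 5.1% = 7.1 points
- pruritus 12.0% − 6.1% = 5.9 points
- asthenia 9.0% − 3.9% = 5.1 points

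These are differences regardless of causality. They show that events an investigator might attribute to RBV are not rare; they do not estimate the gap.

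**How many subjects does it touch?** All GT1a and all cirrhotic subjects receive RBV (Protocol 5.1.2), so only non-cirrhotic GT1b subjects do not. With 100 to 150 cirrhotic subjects among 600 there are 450 to 500 non-cirrhotic. The GT1b share is not given; I assume 25% to 40%.

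- Low end: 600 − 0.40 × 500 = 400.
- High end: 600 − 0.25 × 450 = 487.5, about 490.

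On that assumption, RBV causality is assessable in roughly 400 to 490 subjects. This too says nothing about the size of the gap.

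**The case against.** The strongest reply is that a table labelled DAA-related is correct when it leaves out RBV-only events. That stands. The defect is a missing table, not a wrong one.

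It is also fair that RBV toxicity is not hidden. Every such event enters the all-causality tables. Events leading to RBV dose modification are tabulated in SAP 11.2.1.1. SAP 8.0 counts RBV modifications for falling hemoglobin and RBV interruptions. SAP 11.3.2 summarizes hemoglobin by toxicity grade with a listing. None of these replaces a relatedness table, since they rest on occurrence, action taken or laboratory values, but the anemia example would be seen elsewhere in the report.

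On missing causality, Protocol 6.3 can be read as a sponsor classification, whereas the SAP table reports the investigator's own assessment. Both documents also rule out imputing safety data apart from listed exceptions (Protocol 8.1, SAP 6.3). The SAP ordering is not lenient: unknown overrides a rating of no reasonable possibility, and the unknown row is displayed, so a reader can bound the count for each preferred term. This weakens the secondary point without removing it, because 6.3 states no limit on its scope.

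Three stronger readings are tempting and not supported:

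- *Drug-related rates are under-reported or biased downward.* Only equal or lower can be shown.
- *About 97% of anemia drops out,* from (7.5 − 0.2) / 7.5. That is an all-causality excess between arms, not the share attributed to RBV alone.
- *Missing causality is excluded from every reasonable-possibility table.* The SAP states its rule only for the maximum-relationship table.

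**Conclusion.** The omission is established by the text and needs no assumption. RBV is study drug, its causality is collected, a tabulation by relationship to study drug is promised, and the SAP plans none that includes RBV. The effect on the reported drug-related rate is one-directional and of unknown size, possibly zero.

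The missing-causality conflict is real but minor. It calls for reconciling the two rules and does not support a finding of bias.

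The point should be corrected before the safety tables are produced. The primary efficacy analysis is unaffected, and no between-arm comparison depends on these tables.

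**What to change.** In SAP 11.2.1.1:

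1. Add reasonable-possibility summaries for relationship to RBV, with subjects who received RBV as the denominator.
2. Add the same for relationship to any study drug (DAA or RBV), and use this version as the tabulation that Protocol 8.1.4.1 calls for.
3. Keep the DAA tables as they are.
4. Reconcile missing or not assessable causality with Protocol 6.3. Either count such events as related in the relatedness tables, with a footnote giving the number so assigned, or keep the unknown row and add a sensitivity count that treats them as related. State which rule applies in all relatedness tables, not only the maximum-relationship one.

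The cost is some SAP wording and a few extra tables; no new data are needed. The reported drug-related rates may come out slightly less favourable.

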11.2.2 Listing of Adverse Event

Listings of all serious adverse events (from the time the subject signed the study-specific informed consent until end of study), treatment-emergent serious adverse events, treatment-emergent adverse events leading to death, treatment-emergent adverse events leading to discontinuation of study drug, treatment-emergent adverse events leading to study drug interruptions, and treatment-emergent adverse events of special interest will be provided.

11.3 Analysis of Laboratory Data

Data collected from central and local laboratories, including additional lab testing due to all SAE will be used in all analysis.

11.3.1 Variables and Criteria Defining Abnormality

Hematology variables include: hematocrit, hemoglobin, red blood cell (RBC) count, white blood cell (WBC) count, neutrophils, bands, lymphocytes, monocytes, basophils, eosinophils, platelet count, absolute neutrophil count (ANC), reticulocyte count, PT/INR, and activated partial thromboplastin time (aPTT).

Chemistry variables include: blood urea nitrogen (BUN), creatinine, total bilirubin, direct and indirect bilirubin, serum glutamic pyruvic transaminase (SGPT/ALT), serum glutamic oxaloacetic transaminase (SGOT/AST), alkaline phosphatase, sodium, potassium, calcium, inorganic phosphorus, uric acid, cholesterol, total protein, glucose, triglycerides, albumin, chloride, bicarbonate, magnesium, gamma glutamyl transferase (GGT), total insulin, calculation of estimated glomerular filtration rate (eGFR) using the modification of diet in renal disease (MDRD) equation as defined below, calculated creatinine clearance (eGFR by Cockcroft-Gault calculation), alpha2-macroglobulin, haptoglobin, and apolipoprotein A1.

Urinalysis variables include: specific gravity, ketones, pH, protein, blood, glucose, urobilinogen, bilirubin, leukocyte esterase, albumin, and microscopic (reflexly performed if other variables are abnormal).

The following calculation is used for eGFR by MDRD, where serum creatinine is measured in mg/dL and age is measured in years:

$$\text{GFR (mL/min/1.73 m}^2\text{)} = 175 \times (\text{Serum Creatinine})^{-1.154} \times (\text{Age})^{-0.203} \times 1.212 \text{ (if Black)} \\ \times 0.742 \text{ (if Female).}$$

The Criteria for Potentially Clinically Significant (PCS) Laboratory Findings are described in [Table 8](#) and [Table 9](#).

Table 8. Criteria for Potentially Clinically Significant Hematology Values

Test/Units	Very Low (VL)	Very High (VH)
Hemoglobin		
(mmol/L)	< 4.9	
(g/dL)	< 8.0	
(g/L)	< 80	
Platelets Count		
(cells/mm ³)	< 50,000	
(cells/L)	< 50 × 10 ⁹	
White Blood Cell Count		
(cells/mm ³)	< 2000	> 20,000
(cells/L)	< 2.0 × 10 ⁹	> 20 × 10 ⁹
Absolute Neutrophil Count		
(cells/mm ³)	< 1000	
(cells/L)	< 1 × 10 ⁹	
Lymphocyte Count		
(cells/mm ³)	< 500	
(cells/L)	< 0.5 × 10 ⁹	
Eosinophil Count		
(cells/mm ³)		> 5000
(cells/L)		> 5 × 10 ⁹
aPTT	> 2 × ULN	
International Normalized Ratio	> 2 × ULN	

Note: A post-baseline value must be more extreme than the baseline value to be considered a PCS finding.

Table 9. Criteria for Potentially Clinically Significant Chemistry Values

Test/Units	Very Low (VL)	Very High (VH)
ALT/SGPT		$> 5 \times \text{ULN}$ and $\geq 2 \times \text{baseline}$
AST/SGOT		$> 5 \times \text{ULN}$ and $\geq 2 \times \text{baseline}$
Alkaline Phosphatase		$> 1.5 \times \text{ULN}$
Total Bilirubin (mg/dL)		$\geq 2.0 \times \text{ULN}$
Creatinine		
(mcmol/L)		≥ 132.605
(mg/dL)		≥ 1.5
Creatinine Clearance (mL/min)	< 50	
BUN	$> 5 \times \text{ULN}$	
Uric Acid		
(mcmol/L)		> 713.817
(mg/dL)		> 12.0
Phosphate		
(mmol/L)	< 0.6	
(mg/dL)	< 2.0	
Calcium, Serum		
(mmol/L)	< 1.75	> 3.1
(mg/dL)	< 7.0	> 12.5
Sodium (mmol/L)	< 130	> 155
Potassium (mmol/L)	< 3.0	> 6.0
Magnesium		
(mmol/L)	< 0.4	> 1.23
(mg/dL)	< 0.9	> 3.0
Glucose		
(mmol/L)	< 2.2	> 13.9
(mg/dL)	< 40	> 250
Albumin		
(g/L)	< 20	
(g/dL)	< 2	
Protein		
(g/L)	< 50	
(g/dL)	< 5.0	

Table 9. Criteria for Potentially Clinically Significant Chemistry Values (Continued)

Test/Units	Very Low (VL)	Very High (VH)
Cholesterol		
(mmol/L)		> 10.34
(mg/dL)		> 400
Triglycerides		
(mmol/L)		> 5.7
(mg/dL)		> 500

Note: A post-baseline value must be more extreme than the baseline value to be considered a PCS finding.

11.3.2 Statistical Methods

Clinical laboratory tests will be summarized at each visit during the Treatment Period. The baseline value will be the last measurement on or before the day of the first dose of study drug. This same baseline value will be used for all change from baseline tables in the Treatment Period and Post-Treatment Periods.

Mean changes from baseline to each post-baseline visit, including applicable post treatment visits, will be summarized for each protocol-specified laboratory parameter with the baseline mean, visit mean, change from baseline mean, standard deviation, and median.

Laboratory data values will be categorized as low, normal, or high based on normal ranges of the laboratory used in this study. Shift tables from baseline to minimum value, maximum value, and final values during the Treatment Period (Study Drug End Day ≤ 2) will be created. The shift tables will cross tabulate the frequency of subjects with baseline values below/within/above the normal range versus minimum/maximum/final values below/within/above the normal range.

The number and percentage of subjects with post-baseline values during the Treatment Periods meeting the specified criteria for Potentially Clinically Significant (PCS) laboratory values (defined in [Table 8](#) and [Table 9](#)) will be summarized. A post-baseline

e value must be more extreme than the baseline value to be considered a PCS finding. A separate listing will be provided that presents all lab values for the subjects meeting PCS criteria during treatment.

For hemoglobin and the liver function tests (LFTs) of alkaline phosphatase and total bilirubin, the number and percentage of subjects with a maximum Common Terminology Criteria for Adverse Events (CTCAE) Grade of 1, 2, 3, or 4 (see definitions in [Table 10](#)) at any post-baseline visit (regardless of the baseline value) through the end of treatment (i.e., Final Treatment Value) will be summarized. All LFT tables will include summary rows for the number and percentage of subjects with at least Grade 2 and at least Grade 3 laboratory abnormalities. The hemoglobin table will include a summary row for the number and percentage of subjects with at least a Grade 2 laboratory abnormality.

For the liver function tests (LFTs) of ALT and AST, the number and percentage of subjects with a maximum Common Terminology Criteria for Adverse Events (CTCAE) Grade of 1, 2, 3, or 4 (see definitions in [Table 10](#)) at any post-nadir visit (regardless of the baseline value) through the end of treatment (i.e., Final Treatment Value) will be summarized. Note, for these analyses, the nadir is used for reference instead of baseline. Both ALT and AST tables will include summary rows for the number and percentage of subjects with at least Grade 2 and at least Grade 3 laboratory abnormalities.

Accompanying listing of hemoglobin results will be provided for any subjects with at least Grade 2 hemoglobin abnormalities. Accompanying listings of all ALT, AST, total, indirect and direct bilirubin, and alkaline phosphatase will be created for any subject who had at least a Grade 3 ALT, AST, alkaline phosphatase, or total bilirubin. A listing of the hematology results will be provided for subjects with hemoglobin abnormalities.

Table 10. Definitions of CTCAE Grades 1, 2, 3, and 4

Test	Grade 1	Grade 2	Grade 3	Grade 4
ALT/SGPT	> ULN – 3 × ULN	> 3 – 5 × ULN	> 5 – 20 × ULN	> 20 × ULN
AST/SGOT	> ULN – 3 × ULN	> 3 – 5 × ULN	> 5 – 20 × ULN	> 20 × ULN
Alkaline Phosphatase	> ULN – 2.5 × ULN	> 2.5 – 5 × ULN	> 5 – 20 × ULN	> 20 × ULN
Total Bilirubin	> ULN – 1.5 × ULN	> 1.5 – 3 × ULN	> 3 – 10 × ULN	> 10 × ULN
Hemoglobin Decreased	< LLN – 100 g/L	< 100 – 80 g/L	< 80 – 65 g/L	< 65 g/L

The number and percentage of subjects meeting the following criteria will be summarized:

- ALT $\geq 3 \times$ ULN and total bilirubin value $\geq 2 \times$ ULN;
- ALT $> 5 \times$ ULN (equivalent to Grade 3 or higher) and total bilirubin value $< 2 \times$ ULN.

A subject or event will be counted if the post-nadir laboratory values meet the above criteria regardless of the baseline laboratory value (i.e., the post nadir laboratory value does not need to be worse than the baseline laboratory value). The maximum ratio relative to the ULN will be used to determine if subjects meet the criteria listed above.

For subjects meeting the ALT $\geq 3 \times$ ULN and total bilirubin value $\geq 2 \times$ ULN criterion during the Treatment Period, a corresponding listing of all ALT, AST, alkaline phosphatase, and total, direct, and indirect bilirubin values will be provided.

11.4 Analysis of Vital Signs and Weight

11.4.1 Variables and Criteria Defining Abnormality (If Applicable)

Vital sign variables are body temperature (oral), sitting systolic blood pressure, sitting diastolic blood pressure, sitting pulse rate, and body weight.

The criteria for potentially clinically significant vital sign findings are presented in [Table 11](#).

Table 11. Criteria for Potentially Clinically Significant Vital Sign Values

Test/Measurement	Very Low (VL)	Very High (VH)
Systolic Blood Pressure	≤ 90 mmHg AND A decrease of ≥ 20 mmHg from baseline	≥ 180 mmHg AND An increase of ≥ 20 mmHg from baseline
Diastolic Blood Pressure	≤ 50 mmHg AND A decrease of ≥ 15 mmHg from baseline	≥ 105 mmHg AND An increase of ≥ 15 mmHg from baseline
Heart Rate	≤ 50 bpm AND A decrease of ≥ 15 bpm from baseline	≥ 120 bpm AND An increase of ≥ 15 bpm from baseline
Weight	A decrease of ≥ 15% from baseline	An increase of ≥ 15% from baseline
Temperature		> 38.3°C AND An increase of ≥ 1.1°C from baseline

11.4.2 Statistical Methods

Vital signs will be summarized at each visit during the Treatment Period. The baseline value will be the last measurement on or before the day of the first dose of study drug. This same baseline value will be used for all change from baseline tables in the Treatment and Post-Treatment Periods.

Mean changes from baseline to each post-baseline visit, including applicable post treatment visits, will be summarized for each vital sign parameter with the baseline mean, visit mean, change from baseline mean, standard deviation, minimum, median, and maximum.

The number and percentage of subjects with post baseline values during the Treatment Period meeting Criteria for Potentially Clinically Significant Vital Sign Values (Table 11) will be summarized. A post-baseline value must be more extreme than the baseline value to be considered as a PCS finding. A separate listing will be provided that presents all of the vital sign values for the subjects meeting the PCS vital sign criteria during treatment.

